## **2.6 SAMPLE SIZE ESTIMATION AND SAMPLING PROCEDURES**

The sample size for the quantitative survey is estimated using a two-sided Wald Z-test using GEE methods, accounting for repeated measures and clustering within groups and assumes no change of the estimate for the primary outcome for the study within the comparison group. The primary outcome will be a binary measure, which documents whether the AGYW has met criteria for 'comprehensive' knowledge of what is needed at conception to attain a healthy pregnancy. It will be estimated from a composite measure made from a combination of questions assessing AGYW about their knowledge about behaviors (proper nutrition, screening tests and treatment for HIV and sexually transmitted infections, use of prenatal vitamins, and avoidance of harmful substances). These questions are curated from a systematic review conducted in Ethiopia on the knowledge of preconceptual care and which is also relevant for Nigeria(Ayele et al., 2021). This study established a pooled estimate of good knowledge of preconceptual care of 30.9%. In our study, an AGYW will be comprehensively knowledgeable if she responds to the affirmative to all the questions. The questions will be fielded at the time of recruitment and repeated 3 months later.

To detect an effect size of 10% (between recruitment and 3 months later assuming no change in the comparison group), with a power of 80% at the 95% confidence level (two-sided), we would need a sample size of 991 participants in each country equally split between the comparison and intervention group. This assumes an adjustment of 10% for non-response and a design effect of 1.2. Appendix R (page 57) summarizes sample sizes with different scenarios of estimated effect sizes. We adjust this sample upwards by 10% to account for attrition that might occur between recruitment and the follow-up after 3 months to arrive at a sample size of 1,090 which when split between the groups would be 545 AGYW. Cumulatively for Nigeria and Ethiopia, the final sample size would entail 2,180 participants. This sample is increased by 240 to 2,420 to account for recruitment adjustments for Ethiopia.

A two-group repeated measures design with a binary response and with 2 measurements for each subject will be used to test whether there is a difference in group slopes. The comparison will be made using a Wald Z-test using GEE methods. The repeated measurements of each subject will be made at 2 times and using an autoregressive correlation structure (AR1). The initial proportions  $P1(0)$  and  $P2(0)$  are estimated at 0.3 based on estimates in the literature (preconception care knowledge).  $P2(1)$  proportion assumes no change in the primary outcome over the course of the intervention. Estimates are adjusted by 10% missing/non-response rate and a design effect of 1.2 to account for within community or group clustering.

Table 2 shows estimated total sample sizes for the primary and secondary target populations included in this study.

**Table 2. Sample size estimates for MNCH OE**

	# of participants in Ethiopia	# of participants in Nigeria	Cumulative Sample size	Total samples
Quantitative survey				
Intervention arm	545+116=661	545	1,206	2,420
Comparison arm	545+124=669	545	1,214	
Qualitative component				
FGDs with married AGYW	40*	40	80	173
IDIs with married AGYW	24	24	48	
IDIs with husbands (Nigeria only)	-	10	10	
KIIs with health providers and mobilizers	10	25	35	
Cumulative sample for the study				2,593

\*Each FGD recruits a maximum of 10 participants

## 2.7 DATA COLLECTION PROCEDURES

### 2.7.1 Quantitative survey

Upon receipt of the confidential recruitment lists from mobilisers, trained enumerators from VKM and Deep Dive Research and Consulting PLC will contact the potential participants to arrange for the interview date and time (using Information Sheet in Appendix G) as explained in 2.4.1. This will be done through a phone contact or a physical visit to the participant's residential address. In case it is a call, enumerators will ensure that only when the AGYW is comfortable to speak and in a location that guarantees auditory privacy before that can proceed and make the scheduling call. As they schedule the interview, enumerators will guide the AGYW to elect where they would be comfortable to take the interview between a selected community safe space, a health facility or at their residence. Enumerators will also remind participants that it is voluntary to participate. For Oromia region, a slight modification will be made so that enumerators will confirm pregnancy status (as they administer the information sheet during the call), as soon as the sample of non-pregnant girls allocated to them has been reached. This will prevent them from exceeding the sample quotas.

On the date of the baseline interview and upon arrival at the venue for the interview, the enumerator participant will confirm that the location offers auditory and visual privacy and ensure everything is ready. When the AGYW arrives, the enumerator will introduce herself (all interviewers will be conducted by trained young women for gender sensitivity). Before executing the interviews, the

enumerator will perform detailed consenting procedures. During the consenting the enumerator will explain to the participant why obtaining contact details to facilitate future follow-up is necessary. This will also include explaining the reasons for obtaining secondary contact information, details about how it will be used and what will be said to camouflage the real details of the study. They will also be informed about sharing of the de-identified data in a data repository. Informed consent of the participant will then be obtained, and a signature or thumb print impression made on a consent form. For both emancipated minors and girls with legal right to consent, the same document will be used to obtain consent. After consent is obtained and the enumerator verifies that there is auditory and visual privacy, she will conduct the interview. When she has completed the interview, the enumerator will provide adequate information about the follow-up surveys and obtain contact and physical locator information for the purpose of these surveys.

Before participants leave, they will be issued a unique Study ID and given a study Contact Card (**Appendix O**) on which this number is written (no names will be written on the card). The Card will also bear contact details of In-Country Lead Investigator and contact details of the local REB that has approved the study just in case girls want to follow-up to receive additional information about their rights to participation. The enumerator will record the participants details (name, contact address- primary and alternative or secondary (another phone number through which a participant can be reached if their main contact number is not working), physical address and Study ID) in a password protected electronic study tracking register hosted on the data collection devices (institutionally-owned) which will be serially completed. This information will enable the confirming of the identity of the participant at the follow-ups. Once data is captured on the electronic tracking register (**Appendix P**), the data collector will not be able to edit the entries, nor will the entries be downloadable. The tracking register will be hosted in secure cloud in SFH and PSI's SharePoint and only the PI will have authority to decrypt the entries- once the time for the follow-ups start. Once all the girls in the confidential contact lists used during recruitment have been engaged, these lists will be destroyed immediately. The survey questionnaire will be hosted on the Open Data Kit (ODK) platform, specifically SurveyCTO. Survey CTO is a secure android-based data collection platform that enables remote data collection and permits intermittent synchronization with a secured server. Data will be submitted to the server at least once in a day.

During follow-up, the enumerators will be provided access to the decrypted registers and only the specific record they are responsible for. They will be expected to contact participants two weeks before the expected date of the follow-up interview (after 3 completed months after the initial interview and 8 complete weeks after the expected date of delivery – pregnant AGYW only). As a rule, enumerators will employ the participant's primary contact details. We will only use secondary contact details if the use of the primary contact details is unsuccessful or impossible as can occur if the AGYW doesn't own a phone. Enumerators will attempt at most five times if the mobile contact is not going through or is not picked. During these calls, the enumerator will first introduce

herself, then confirm that the person speaking on the other side is the AGYW, establish that the AGYW is comfortable to speak and has auditory privacy before she can proceed. Enumerators will be guided by the follow-up script (**Appendix S**). During the call, enumerators will also remind participants that it is voluntary to participate in the follow-up interviews.

We will also use locator information (physical address details) collaborating with mobilizers to physically locate participants from their residences and schedule dates for interviews. For participants who are reached on phone, the exact date and venue of the interview will be decided by the participant, ensuring that convenience of the participant is prioritized. In much as possible we will suggest that enumerators synchronize the interview date to clinic visits or when the AGYW visit places near the study site such as market days.

During these follow-up calls, if a participant has provided phone details of another person, enumerators will ask to speak to the participant without disclosing the exact reasons why we are calling her (citing that we are conducting a general health wellbeing follow up from the nearest health facility) and without using terms such as sexual and reproductive health or family planning. If the participant is not within the proximity of the person who received the call when the phone call is made, the enumerator will leave a message that the participant could call or beep back the enumerator's number when she is available so that the enumerator can initiate the call. Only when the enumerator is assured that the participant is the one on the other side and has auditory privacy will the conversation continue. Otherwise, enumerators will ask the participant to suggest a safer time when they could call back. AGYW who are not reached within a one-month period since their due date for follow-up will be designated as lost to follow-up and the exact reason for not being reached documented in their study record.

When contacted for follow-ups, participants shall be sensitized on the available options where the data collection could take place so that they can voluntarily select their preferred venue and are familiar with what to expect. At data collection, the unique Study ID of the participants documented in the tracking register will again be entered into the Survey CTO system. Enumerators will confirm participant details through the electronic register that was created at recruitment and also using the Study Contact Card that was given to the participant at the same time. AGYW will be encouraged to carry their Contact Cards when they turn up for follow-ups, although it will not be a mandatory requirement for participation since the register will be sufficient. Once data collection is completed, participants will be appreciated, and an entry made on the register that a follow-up has been completed.

As explained earlier the second follow-up will target AGYW who are pregnant at baseline and those found to be pregnant at the first follow-up (if they were not pregnant at baseline). The participant tracking register will be customized to auto-calculate the expected date of delivery (EDD) (using Naegele's rule) using the last menstrual period as a reference (Edwards & Itzhak, 2019). The register will then estimate 8 completed weeks from this date. This will be a rough estimate from

the date of delivery as the EDD is an approximated value subject to error. This follow-up will be done on the first date of week 9 since the EDD. As with the first follow-up, the enumerator will be prompted to initiate a scheduling call two weeks before this date. They will use the follow-up script, but in this case, they will say the information specific for this follow-up. Enumerators will be thoroughly trained to identify and handle scenarios where AGYW are uncomfortable to schedule an interview that might be speaking about a pregnancy that had an unfavourable outcome. To manage the sensitivities of this follow-up, voluntary participation and withdrawal will be emphasized during the calls, visits and when conducting the interview. This will reduce pressure on the AGYW who are uncomfortable from participating when they do not.

The follow-up interviews will follow the same format as the initial interview though the questions will be slightly different. Once a follow-up is completed, no entries will be possible on the same study record. Some attrition is to be expected, but measures will be taken to reduce this as much as possible. This includes multiple call attempts using the primary and secondary contacts, use of physical tracing with the help of trained mobilizers and provision of a small stipend (equivalent to \$2 in local currencies (Naira for Nigeria and Birr for Ethiopia) given in cash for each successful baseline and follow-up interview) to reimburse for transport incurred to visit the data collection location. Those who participate in phone follow-up interviews will receive \$1 airtime on their phones. Immediately after all the follow-ups are completed the registers will be destroyed by the PI. Participants will not be required to sign any document to confirm the receipt of the reimbursements, neither will their personal details be captured in a study document to account for the money reimbursed for transport or send as airtime to your phone. Instead, research assistants will sign against a document that summarizes the number of participants who have received the reimbursement or airtime without capturing any personal information. The field supervisors from VKM and Deep Dive Research and Consulting PLC will countersign the summary document for each study site to affirm that the cumulative amount of reimbursements given matches the number of participants interviewed. This summary will be submitted to the finance departments to account for the resources received.

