### **1.3 DESCRIPTION FOR THE MNCH COMPONENTS**

#### **Expanded MMA with MNCH**

In northern Nigeria, MMA is supported through the Society for Family Health and is implemented through primary care centres (PHCs) in four states: Kaduna, Nasarawa, Jigawa and Kano. MMA targets married adolescent girls who are mobilized through trained female mentors who directly engage girls in the communities and link them to MMA-supported PHCs. Additionally, trained male interpersonal communication agents (MIPCAAs) engage men in spots where they congregate to illustrate the value of birth spacing to attaining good health of the mother and the child. Men who express interest in birth spacing are given referral cards to give to their wives, who walk into PHCs to receive counselling and services. At the PHCs girls receive services directly through a trained youth-friendly provider and could participate in life, family and health (LFH) classes. LFH consists of four guided mentorship sessions conducted over a four-week duration convened by trained mentors. During these sessions girls receive information including nutrition, child spacing, interpersonal communication, financial management and gains life and vocational skills(Sarah. et al., 2021).

The MNCH component for MMA is built on the LFH classes. Girls who are at risk of pregnancy and who don't want to use a method of contraception or who suspect that they are pregnant are mobilized by female mentors or through their husbands to attend LFH sessions at PHCs. Those who walk in to receive services are offered the services directly and introduced to the LFH classes. The sessions take two hours, are moderated by trained female mentors and attended by ANC experts (trained providers) who offer information and counselling on attaining health pregnancies. MIPCAAs facilitate community sessions with men whose wives (15-19) are pregnant and refer them to access ANC services. All mobilized girls who test positive for pregnancy undergo routine ANC, enhanced with gestational age-specific messages about the expectations of ANC, birth preparedness, nutrition during pregnancy, danger signs and how to avoid them and postpartum family planning (PPFP).

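### The protocol suggests timing follow-up interviews to clinic visits without placing them before that day's counselling, so some 3-month knowledge measurements may be same-day post-tests that differ by arm

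*Protocol*

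**What the plan says.** Section 2.6 fixes the timing of the primary outcome, a binary measure of comprehensive knowledge that requires every item to be affirmed: "The questions will be fielded at the time of recruitment and repeated 3 months later".

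Section 2.7.1 covers how follow-up interviews are arranged. As far as possible, "we will suggest that enumerators synchronize the interview date to clinic visits", and the same sentence offers trips near the site, such as market days, as the alternative. The sentence before it says that, for participants reached by phone, "the exact date and venue of the interview will be decided by the participant, ensuring that convenience of the participant is prioritized". Mobilizers also help to "physically locate participants from their residences and schedule dates for interviews", and venue options are explained to participants "so that they can voluntarily select their preferred venue and are familiar with what to expect". On loss to follow-up: "AGYW who are not reached within a one-month period since their due date for follow-up will be designated as lost to follow-up".

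Section 1.3 describes what happens at the facilities. In Nigeria, LFH classes run at PHCs, and mobilized girls who test positive for pregnancy "undergo routine ANC, enhanced with gestational age-specific messages about the expectations of ANC". In Ethiopia, girls who may be pregnant go through a seven-step counselling process at health centres or health posts. Section 2.2 places the comparison group where MMA or Smart Start runs without the MNCH component.

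Section 2.9.1 analyses outcomes by difference-in-difference, with a GEE Wald test for the primary outcome, and attributes significant follow-up differences to the intervention, within reason.

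**The concern.** The treatment under test is largely information given at facility contacts, and the primary endpoint tests knowledge. An interview held on a clinic day, after the session, measures recall of something just heard. In the comparison arm the same contact carries the current package only, so the recall gain need not be equal between arms.

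Differencing against baseline would remove this only if baseline interviews had the same relation to clinic contact. The clinic-visit suggestion is written for follow-up alone. The Summary also describes eligible girls as not having started ANC (Table 1 does not list that criterion), so a baseline interview straight after ANC counselling should be uncommon.

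At stake is the meaning of the endpoint. Knowledge at three months would be mixed, for an unknown share of participants, with an immediate post-test, and the slope contrast would credit the mixture to the intervention.

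**Working it through.** **Step 1. Is the interview ordered relative to the session?** Sections 2.4.1, 2.7.1 and 2.8 contain no rule that the interview precede the session, no minimum gap, and no item recording the order. Section 2.8.1 collects GPS coordinates, which show where an interview took place but not whether it followed a session, and they are stripped during cleaning.

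**Step 2. Can clinic days be common at three months?** About 70% of the sample is meant to be pregnant (Summary), at no more than 24 weeks at entry (Table 1). Many would still be pregnant three months later, when ANC visits occur. The documents do not give the share of interviews on clinic days.

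**Step 3. The plan's own sample size.** This calibrates the standard error. Inputs from section 2.6: 0.3 to 0.4 against 0.3 to 0.3, two-sided 5%, 80% power, 10% non-response, design effect 1.2. The within-subject correlation is not given in the text shown.
- Logit scale, assumed correlation 0.5: 372 per arm, and 372 × 2 × 1.2 / 0.9 = 992, against the stated 991.
- Identity scale, assumed correlation 0.45, with non-response applied as a factor of 1.1: also 992.
- Attrition: 991 × 1.1 = 1,090, or 545 per arm, as stated.

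**Step 4. Shift in the contrast.** With share s of interviews held after same-day counselling and recall gain g:

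shift = s(intervention) × g(intervention) − s(comparison) × g(comparison)

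Both s and g are assumptions. The table sets the comparison term to zero.

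**Step 5. Chance of a significant result with no lasting effect.** Effective number per arm = 545 × 0.9 × 0.9 / 1.2 = 367.9. With p = 0.3 throughout and correlation 0.45, SE = √[0.42 × 2 × (1 − 0.45) / 367.9] = √(0.462 / 367.9) = 0.0354. The rejection probability is 1 − Φ(1.96 − shift/SE) + Φ(−1.96 − shift/SE).

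| Share on counselling day | Gain 5 points | Gain 10 points | Gain 15 points |
|---|---|---|---|
| 20% | 1.0 pt; 5.9% | 2.0 pt; 8.7% | 3.0 pt; 13.5% |
| 40% | 2.0 pt; 8.7% | 4.0 pt; 20.4% | 6.0 pt; 39.5% |
| 60% | 3.0 pt; 13.5% | 6.0 pt; 39.5% | 9.0 pt; 71.9% |

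A comparison-arm gain would reduce these figures. For instance, with equal shares of 20% and gains of 20 and 5 points, the shift is 0.20 × 20 − 0.20 × 5 = 3 points.

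**Step 6. Easier scheduling of attenders.** Assume half of an arm are clinic attenders with 45% knowledge against 25% in the rest, so the true value is 35%.
- Completion 95% against 85%: (0.5 × 0.95 × 45 + 0.5 × 0.85 × 25) / (0.5 × 0.95 + 0.5 × 0.85) = 35.6%, a shift of 0.56 points.
- Completion 95% against 75%: 36.2%, a shift of 1.18 points.

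This is a shift within one arm; only a difference between arms enters the contrast.

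**The case against.** **It is a suggestion, with an alternative.** Market days are named in the same sentence, and participants reached by phone choose date and venue. This stands: a reader might infer that enumerators are instructed to interview at clinics, and the text does not say that. Even so, a preference that operates as far as possible will move some interviews to clinic days.

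**Completion does not hinge on clinic attendance.** A reader might infer that it does, especially from the one-month loss rule. The documents do not support that. Loss means not being reached, and section 2.7.1 provides repeated calls, secondary contacts, tracing at home, a choice of venue and phone interviews. At most, attenders are easier to schedule, which step 6 puts at about a point or less.

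**The overlap in content is limited.** LFH lasts four weeks and may be over by three months. For non-pregnant girls in Ethiopia the health extension worker contact is not tied to a facility. The enhanced ANC messages listed for Nigeria clearly share only nutrition with the primary composite. This stands as a reason to doubt the large gains in the table. It does not remove the mechanism: under an all-items rule, a girl who lacks one item can change status on that item alone.

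**Baseline is not clinic-free.** Mobilizers may approach girls in clinics, and a facility is an offered venue. True, but the interview is arranged separately from the recruitment list, and no clinic-visit preference is written for baseline.

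**Clinic contact is part of a real-world intervention.** The contact is. Choosing the measurement date because of the contact is a separate decision, and section 2.6 places the measurement at three months.

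**Conclusion.** The point holds in a limited form. The protocol leans follow-up interviews, including the one behind the primary endpoint, towards occasions when the counselling under test may be given. It sets no order between the two, and the content differs by arm. Any same-day recall gain would therefore stay in the difference-in-difference.

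The documents cannot show that the bias will occur or how large it would be. The 1-9 point range against a 10-point design effect depends entirely on assumed shares of 20-60%, assumed gains of 5-15 points and no gain in the comparison arm. The rejection rates of about 6-72% add an assumed correlation of 0.45 and the planned 545 per arm. The limited overlap in content makes the upper end harder to credit. No single figure in the range should be read as an estimate, and the stated sample size is unaffected. Selection through easier scheduling is secondary.

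**What to change.** In section 2.7.1, for the 3-month interview:

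- Prefer market days or other neutral occasions to clinic visits.
- Where an interview does fall on a clinic day, hold it before any consultation or group session that day.
- Add one SurveyCTO item recording whether it was a clinic day and, if so, whether the interview came before or after the session.
- Repeat the primary contrast without interviews held after a session. This is a sensitivity analysis only: clinic attendance may itself respond to the intervention, so the exclusion can introduce selection of its own. Interviewing first is the main protection.

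The cost is a sentence or two in the protocol, a line in enumerator training and one data item. Scheduling becomes slightly less convenient, and somewhat more interviews will take place at home or in safe spaces, under the privacy safeguards already planned. Home tracing, residence interviews and the $2 reimbursement are already in the plan, which limits the risk to retention. Participants keep their choice of date and venue, and the care they receive is untouched.
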